6.1.2 Primary Effectiveness Endpoint

The primary effectiveness endpoint is wart clearance, defined as “resolved” versus “not resolved” at 30 days following the last CellFX or Cryosurgical treatment (30 days post-last treatment) based on the classification of the blinded site investigator. The timing of the evaluation of this endpoint is wart specific as some warts may not require more than 1 treatment with the CellFX System or Cryosurgery. The investigator, blinded to treatment assignment, will classify each wart as “resolved” or “not resolved”.

The primary effectiveness analysis will be a comparison between CellFX and Cryosurgical treatment groups based on 30-day post treatment clearance rate, defined as the proportion of warts classified as “resolved”. This binary outcome classifies warts as completely clear versus not completely clear. The 30-day time-point was selected to reduce the impact of spontaneous wart resolution unrelated to treatment.

The statistical hypotheses to be evaluated for the primary efficacy endpoint are:

$H_0: p_{CellFX} - p_{Cryo} \leq -15\%$ at 30 days post last treatment, versus

$H_A: p_{CellFX} - p_{Cryo} > -15\%$ at 30 days post last treatment

Where p_{CellFX} and p_{Cryo} are the proportion of warts classified as “resolved” in each treatment group. The null hypothesis will be rejected if the lower bound of the 2-sided 95% confidence interval for the difference in proportions ($p_{CellFX} - p_{Cryo}$) is greater than -15%, which is equivalent to a 1-sided test with a 2.5% type I error rate.

6.1.3 Justification of Non-Inferiority Design and Margin

The selection of a non-inferiority design for this study is based on the choice of an active comparator (cryosurgery), the acceptability of the design to subjects seeking treatment for common warts, and feasibility considerations¹¹. Although cryosurgical treatment for warts was found to have numerically higher efficacy compared to placebo¹⁵, the many variations in timing, frequency and delivery of cryosurgery preclude a meta-analysis-based margin derivation for the technique selected for this study. Safety outcomes are inconsistently reported in publications, and no estimates of the composite endpoint of skin changes proposed for this study was available. Thus, non-inferiority margins of 15% were selected based on clinical judgement for the primary safety and effectiveness endpoints. Clinical justifications for this non-inferiority margin

for safety include existing CellFX safety data that demonstrate no serious adverse events, and a comparable safety profile compared to the predicate devices for this indication with the suggestion of faster healing. Clinical justifications for a 15% non-inferiority margin for effectiveness include consistency of treatment and ease of use with the CellFX system.

6.1.4 Type I Error Control and Study Success

Study success requires the demonstration of non-inferiority for the primary safety and efficacy endpoints.¹¹ Thus, no type I error adjustment for multiple testing is required. No formal hypotheses will be tested for secondary endpoints.

6.2 Secondary Endpoints

Details of the planned analyses for secondary endpoints can be found in the statistical analysis plan. No formal hypotheses will be tested for secondary endpoints. The ITT population will be used for all analyses of secondary endpoints.

1. Wart Resolution Determined by Photographic Review

Wart resolution will be assessed by three independent observers, blinded to treatment assignment, who will classify the response for each wart based on photographs taken at 30 days post last treatment. The 3 observers will classify each wart as “resolved” or “not resolved” described in **Section 6.1.2**. The wart will be classified as “resolved” if 2/3 blinded observers classify the wart as “resolved”, and as “not resolved” if 2/3 blinded observers classified the wart as “not resolved”. The difference in proportion of warts classified as “resolved” will be assessed using the GEE model as described in the statistical analysis plan with the photo review endpoint replacing the endpoint derived from the blinded site investigator classification.

2. Wart Resolution after Single Treatment

The proportion in each treatment group and the difference in proportion classified as “resolved” between CellFX and Cryosurgery assigned by the blinded site investigators at 30-days post initial treatment (as opposed to the efficacy endpoint, which is 30 days post last treatment) will be assessed using the GEE model described in the statistical analysis plan with the 30 day endpoint classified by the blinded site investigator.

3. Wart Resolution at 60 Days Post Last Treatment

The proportion in each treatment group and the difference in proportion classified as “resolved” between CellFX and Cryosurgery assigned by the blinded site investigators from baseline to 60-days post last treatment will be assessed using the GEE model described in the statistical analysis plan with the 60 day post last treatment endpoint based on the blinded investigator classification as “resolved” or “not resolved”.

4. Within Subject Effectiveness

The ratio of cleared warts (classified as “resolved”) to all treated warts will be calculated at 30 days post last treatment. The proportion of subjects with complete clearance of all warts (ratio 1) will be calculated for each treatment group, as well as the proportions with > 50% and > 75% of treated warts cleared.

5. Change in Wart Size

The mean difference in reduction from baseline in wart size of treated warts at 30 days post last treatment will be calculated using a mixed model for repeated measures, with treatment, number of warts stratification and baseline size included as fixed effects. An exchangeable correlation matrix will be used to adjust for within-subject correlation. Least-square mean change, difference, and 95% confidence intervals will be calculated from this model.

6. Wart Resolution Over Time

The rate of wart resolution of the treated warts over time and up to 90 days post last treatment will be calculated.

7. Lesion Observations

Lesion observations at 7-days, 30-days, 60-days, and 90-days post last treatment between CellFX and Cryosurgery. Lesion evaluation includes the following:

- Blister Formation
- Bruising
- Crusting
- Erythema
- Hyperpigmentation
- Hypopigmentation
- Scabbing
- Scarring
- Swelling or Edema
- Ulceration

The rate of each event individually and a composite of any of these events will be calculated for each treatment using the GEE model described in the statistical analysis plan, along with the 95% confidence interval as described for the primary safety endpoint.

8. Satisfaction with Treatment

A 6-point Treatment Satisfaction Scale will be used to measure subject's satisfaction with the treatment of each wart.

[figure not shown]
Table 3: Treatment Satisfaction Scale

Rating	Description
6	Very Satisfied
5	Satisfied
4	Somewhat Satisfied
3	Somewhat Dissatisfied
2	Dissatisfied
1	Very Dissatisfied

The proportion with each response will be summarized. An analysis will be performed using the binary endpoints of satisfied ("Very Satisfied" or "Satisfied") versus not satisfied ("Somewhat Satisfied", "Somewhat Dissatisfied", "Dissatisfied", "Very Dissatisfied") to compare satisfaction across treatment groups. As with treatment-level clearance, the counts and proportions of warts categorized as satisfied will be reported. A GEE model to estimate the treatment difference in the proportion of warts with satisfactory treatment will be performed using the methods described in the statistical analysis plan.

9. Acute Pain Assessment

Face Pain Scale with an assigned numerical rating between 0 (smiling) and 10 (crying) will be used to assess pain immediately after the CellFX and Cryosurgical treatments at Day 0, and Days 30, or 60, if applicable. The face pain scale will be assessed immediately after each wart treatment. Please see pain scale chart on the next page.

The number and percent will be tabulated for each level of pain for first, second, or third treatments separately. A histogram of scores will be produced. If the scores are not markedly skewed, mixed models using score as a continuous dependent variable and treatment as a fixed covariate (adjusted for within-subject correlation) will be used to compare the least-square mean difference in pain scores across treatment groups. A model including all treatments and adjusted for treatment number (initial, first retreatment, second retreatment) may be performed for comparison, convergence permitting.

6.3 Sample Size Determination

Power for the primary endpoints was assessed and calculated using the formula for standard non-inferiority designs¹² and then inflating the total number of warts required to account for correlation within subjects.¹³ Several assumptions were estimated using a previous study of warts.⁸ An average of 3 eligible warts per subject was assumed, based on the median number of observed common warts.

The efficacy response rate (classified as “resolved” versus “not resolved”) was approximated using the complete clearance rate for common warts, yielding an estimated CellFX clearance rate at 30 days post last treatment of 75.5%. The within-subject correlation for this endpoint was estimated to be 0.3. The composite wound healing safety event at 30 days post last treatment was estimated to be 37.6%, and the within-subject correlation was estimated to be 0.55. The composite skin change safety event rate at 90 days post last treatment was estimated to be 32.5%, and the within-subject correlation for this endpoint was estimated to be 0.55. For cryosurgery, the 30 day post last treatment clearance rate was estimated to be 70%^{14,10} and the 90 day post last treatment safety event rate was estimated to be 40% (based on 29% hypopigmentation reported and 11% hyperpigmentation assumed).¹⁵ The wound healing safety event rate for cryotherapy was assumed to be 43%. The within-subject correlation for warts was assumed to be identical for CellFX and cryosurgery. No type-1 error adjustment is needed to account for multiple endpoints as the effectiveness response rate and safety event rate are co-primary. In order to maintain at least 88% power to test the primary hypotheses using 15% non-inferiority margins, approximately 97 warts (33 subjects) would be required in each arm. After accounting for within-subject correlation, at least 63 subjects (189 warts) are needed in each arm. To account for approximately 15% loss to follow-up, a total of 150 subjects will be enrolled.

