4.2 Subject Selection

4.2.1 Inclusion Criteria

Candidates for this study must meet **ALL** the following criteria:

1. Subject is at least 18 and no older than 80 years of age.
2. Subject has a Fitzpatrick Skin Type I, II, III or IV.
3. Subject gives voluntary, written informed consent to participate in this clinical investigation and from whom consent has been obtained.
4. Subject must comply with study procedures including all follow-up visits.
5. Subject is willing to have warts treated in a single treatment session and understands that their warts may undergo multiple treatment sessions at subsequent visits.
6. Subject must have a minimum of 2 warts and up to 8 warts to be treated.
7. Subject with a clinical diagnosis of common warts located on hands and fingers or other body areas that are not located on the scalp, nose, within the orbital region of the face, plantar, genital or periungual area.
8. For study purposes, the warts must be no greater than 3 mm in height and must not exceed 10 mm x 10 mm at their largest dimension.
9. Each wart must appear alone and discrete and not appear in clusters.
10. Each wart must have been present for at least 4 weeks.
11. Subject consents to have photographs taken of the warts.
12. Subject agrees to refrain from taking an antihistamine including those used for gastric symptoms(e.g., Loratadine, Desloratadine, Cetirizine, Fexofenadine, Levocetirizine, Azelastine, Ranitidine, Cimetidine, Famotidine, and Nizatidine) up to 48 hours before enrollment and each scheduled follow-up visit, to facilitate an adequate wash-out period.
13. Subject agrees to refrain from using all other wart removal products or treatments (e.g. topical medication including over-the-counter medications) during the study period.

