6.6 Missing Data

All possible efforts will be made to minimize missing data in this study. Based on previous studies, any missing data that does occur is likely due to missed follow-up visits, so all study warts for subjects with a missed visit will have missing endpoints. The timing of the co-primary effectiveness and wound healing events at 30 days should minimize missed visits related to study fatigue. The generalized estimating equation model can yield valid results when data are missing completely at random, and the sensitivity analysis using a mixed model can yield valid results when data are missing at random. Additionally, the sensitivity of the final results to missing data for the skin change safety outcome will be examined by comparing the primary outcomes to the results using a longitudinal model with both the 30-day, 60-day and 90-day post treatment results, and a tipping-point analysis will be performed for the endpoints at 90 days to determine whether the missing data could change the inference compared to the primary models.

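### Section 6.3 claims at least 88% power with 63 subjects per arm, but on its own inputs the wound-healing co-primary has about 80%

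*Combined protocol and SAP*

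**What the plan says.** Section 6.3 (Sample Size Determination) gives a single power figure for all primary hypotheses: "In order to maintain at least 88% power to test the primary hypotheses using 15% non-inferiority margins, approximately 97 warts (33 subjects") in each arm. It continues: "After accounting for within-subject correlation, at least 63 subjects (189 warts) are needed in each arm". On enrolment it says: "To account for approximately 15% loss to follow-up, a total of 150 subjects will be enrolled".

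For wound healing with CellFX, the plan gives a correlation of 0.55, in the sentence that begins "The composite wound healing safety event at 30 days post last treatment was estimated to be 37.6%, and the within-subject correlation was estimated to be". For the comparator, "The wound healing safety event rate for cryotherapy was assumed to be 43"%. On cluster size, "An average of 3 eligible warts per subject was assumed, based on the median number of observed common warts".

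The other inputs in Section 6.3 are clearance 75.5% versus 70% with correlation 0.3, and skin change 32.5% versus 40% with correlation 0.55 (CellFX first in each pair). Correlations are taken as equal in the two arms. Sections 6.1.1 and 6.1.2 test each endpoint at one-sided 2.5% with a 15-point margin. Sections 6.1 and 6.1.4 require non-inferiority on all three endpoints for the study to succeed.

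**The concern.** The two safety endpoints share the same margin, correlation and cluster size, but wound healing has the smaller assumed advantage (5.4 points against 7.5) and event rates closer to 50%. It must therefore need more subjects than skin change. One sample size cannot give both of them just 88%, so the 63 has to be checked endpoint by endpoint.

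The stated power implies that each endpoint, taken singly, has at most a 12% chance of failing if the assumptions are true. Because one failure fails the study, the weakest endpoint caps the probability of success. If wound healing is short of 88%, the protocol understates the risk of a failed study. Type I error, margins and the analysis are not involved.

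**Working it through.** **Inputs.** All are from Section 6.3, with alpha and margin from Sections 6.1.1 and 6.1.2. z for one-sided 2.5% is 1.960 and z for 88% power is 1.175, so (1.960 + 1.175)² = 9.828. There are m = 3 warts per subject.

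**Formulas.** Independent warts per arm: n = 9.828 × V / D², where V = p₁(1 − p₁) + p₂(1 − p₂) and D is the margin plus the assumed advantage of CellFX. Subjects per arm: n × DE / 3. Power with s subjects per arm: Φ(D / √(V / n_eff) − 1.960), where n_eff = 3s / DE.

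**Design effect.** The plan does not print one. I used DE = 1 + (m − 1)ρ, which is 1.6 for ρ = 0.3 and 2.1 for ρ = 0.55.

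**Reproducing the plan's figure.** For skin change, V = 0.325 × 0.675 + 0.40 × 0.60 = 0.4594 and D = 0.15 + 0.075 = 0.225. Then n = 89.2, rounded up to 90; 90 × 2.1 = 189 warts; 189 / 3 = 63 subjects. These are exactly the plan's 189 and 63, which supports the inferred design effect and shows which endpoint the number came from.

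**Wound healing.** V = 0.376 × 0.624 + 0.43 × 0.57 = 0.4797 and D = 0.15 + 0.054 = 0.204. Then n = 113.3; 113.3 × 2.1 = 237.9 warts; 237.9 / 3 = 79.3, so 80 subjects. At 63 per arm, n_eff = 189 / 2.1 = 90 and power = Φ(2.794 − 1.960) = Φ(0.834) = 79.8%.

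| Endpoint | V | D | Independent warts for 88% | DE | Subjects per arm for 88% | Power at 63 | at 71 | at 75 |
|---|---|---|---|---|---|---|---|---|
| Clearance | 0.3950 | 0.205 | 92.4 | 1.6 | 49.3 | 94.4% | 96.4% | 97.2% |
| Wound healing | 0.4797 | 0.204 | 113.3 | 2.1 | 79.3 | 79.8% | 84.3% | 86.2% |
| Skin change | 0.4594 | 0.225 | 89.2 | 2.1 | 62.4 | 88.3% | 91.7% | 93.0% |

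Seventy-five per arm is full enrolment with no loss. Seventy-one is an illustrative case of about 5% loss, not a figure from the plan. At the plan's 15% loss (63.75 per arm), wound healing has 80.3%. A beta-binomial simulation of wound healing (20,000 runs) gave 79.5%, 84.1% and about 86% at 63, 71 and 75.

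**The 97-wart step.** Ninety-seven is not the 88% requirement for any endpoint (92.4, 113.3, 89.2). Nor does it lead to 63: 97 × 2.1 / 3 = 67.9 and 97 × 1.6 / 3 = 51.7. The ratio 189 / 97 = 1.95 matches neither design effect. With 97 fully independent warts per arm, power is 89.5% for clearance, 90.5% for skin change and 82.7% for wound healing, so the claim fails before any clustering is applied.

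**Variants for wound healing at 63 per arm.**
- Variance: pooled 79.7%; restricted (Farrington-Manning) 80.2%; with continuity correction 75.2%.
- Warts per subject, equal in all: 75.7% with 2, 81.9% with 4, and 85.1% with 8, the most that Section 4.2.1 allows ("Subject must have a minimum of 2 warts and up to 8 warts to be treated").
- To reach 88% with the other inputs fixed, the correlation would have to be about 0.33 or the cryosurgery rate about 45.6%.
- One-sided alpha of 5%, contrary to Section 6.1.1, gives 87.5%.

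**The case against.** The best argument on the other side concerns weight and precision, not the core figure.

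- **It is only a planning statement.** No success criterion, estimate or enrolment target changes. That is true, and it is why the fix is wording. But the statement is quantitative, concerns an endpoint that can fail the study alone, and is wrong on its own inputs.
- **The design effect is inferred.** The two methods references cannot be consulted here, and Section 6.0 defers detail to the SAP. The exact 79.8% does rest on the inference. The shortfall does not: the plan's own ratio of 1.95 corresponds to 97 independent warts, which give 82.7%.
- **Attrition may be low.** Section 6.6 says: "The timing of the co-primary effectiveness and wound healing events at 30 days should minimize missed visits related to study fatigue". It gives no rate; the only stated rate is about 15%. With no loss at all, power is still 86.2%.
- **At 75 per arm the gap is within input uncertainty.** This stands. With no loss, 4 equal warts per subject give 88.0%, and at 3 warts a cryosurgery rate of 43.5% or 44% gives 87.7% or 89.1%; the 43% is an assumption without a cited source. The 2-point gap is therefore fragile, while the 8-point gap at the stated 63 is not.
- **Joint power is a separate matter.** Section 6.3 makes no joint claim, so its absence is not an arithmetic error.

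**Conclusion.** The concern holds. On the inputs in Section 6.3, power of at least 88% at 63 subjects per arm is correct for clearance (94.4%) and skin change (88.3%) and wrong for wound healing (79.8%). The gap is 8 points at 63 evaluable per arm, about 4 at 71 and about 2 at 75. The chance of failing wound healing, if the assumptions are true, is about 20% at the planned evaluable size and 14% with no loss, against the implied 12% at most.

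This rests on the printed wound-healing inputs being the intended ones and, for the exact figures, on a design effect of 1 + 2ρ with 3 warts in every subject. Unequal wart counts would lower power slightly: half the subjects with 2 and half with 4 gives 79.0% at 63. The 97-wart and 189-wart figures do not come from one calculation under any of the stated correlations.

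**What to change.** 1. Confirm the wound-healing inputs (37.6%, 43%, correlation 0.55). If one is misprinted, correct it and show the recalculation.
2. If they stand, replace the single 88% with power per endpoint at 63 evaluable subjects per arm: about 94% clearance, 80% wound healing, 88% skin change. Add that wound healing reaches about 84% at 71 and 86% at 75 evaluable per arm, labelling these as about 5% loss and no loss.
3. Replace the 97-wart step with the independent-wart requirements (about 93, 114 and 90 for clearance, wound healing and skin change) and state the design-effect formula used.

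The cost is protocol and SAP wording, and a less favourable stated power for wound healing. Enrolment, margins, endpoints and analysis need not change. If the sponsor instead wants to keep 88% for wound healing on these inputs, it needs 80 evaluable per arm; with 15% loss, 80 / 0.85 = 94.1, so 95 per arm or 190 in total.

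Separately, and of lower priority: since success needs all three endpoints, joint power at 63 per arm could be reported as an assumption-dependent range. It is about 66% if the endpoints are independent (0.944 × 0.798 × 0.883). If the two safety statistics correlate 0.2 to 0.8, which is my assumption (scar is in both composites), it is about 68% to 73%. It cannot exceed about 80% under any dependence.

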6.1 Co-primary Endpoints

Clinical acceptance of treatment with the CellFX System for common warts requires non-inferior clearance response (effectiveness), non-inferior healing processes and non-inferior rates of adverse skin changes (safety) versus cryosurgery. Because these features are critically important for treatment acceptability, this study is designed with 3 co-primary endpoints. The endpoints must demonstrate non-inferiority for the study to be considered successful.¹¹

All 3 co-primary endpoints are assessed with wart as the unit of analysis, but the analyses will be adjusted for within-subject correlation. The co-primary safety endpoints are the proportion of warts with adverse events related to wound healing (scabbing, swelling, crusting, blister, scar or ulcer) at 30 days after the last treatment and adverse skin changes (the presence of hyperpigmentation, hypopigmentation or scarring) at 90 days post last treatment. The co-primary effectiveness endpoint is the proportion of warts classified as “resolved” at 30 days post last treatment.

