6.1.1 Co-primary Safety Endpoints

The wound healing safety endpoint is the presence or absence of a wound healing safety event at 30 days from the last CellFX or Cryosurgical treatment as assessed by the blinded site investigator. The wound healing safety event is defined as the presence of scabbing, swelling, crusting, blister, scar or ulcer. The timing of the evaluation of this endpoint is wart specific as some warts may not require multiple treatments with CellFX or Cryosurgery. Warts will be categorized as having a primary safety event if any component (scabbing, swelling, crusting, blister, scar or ulcer) is present at the follow-up visit 30 days after the last treatment.

The statistical hypotheses to be evaluated for the wound healing primary safety endpoint are:

$$H_0: p_{CellFX} - p_{Cryo} \geq 15\% \text{ at 30 days post last treatment, versus}$$

$$H_A: p_{CellFX} - p_{Cryo} < 15\% \text{ at 30 days post last treatment}$$

Where p_{CellFX} and p_{Cryo} are the proportion of warts with a composite wound healing safety event (scabbing, swelling, crusting, blister, scar or ulcer) in each treatment group. The null hypothesis will be rejected if the upper bound of the 2-sided 95% confidence interval for the difference in proportions ($p_{CellFX} - p_{Cryo}$) is less than 15%. This approach is equivalent to a 1-sided test with a 2.5% type I error rate.

The skin change safety endpoint is the presence or absence of a skin change safety event at 90 days from the last CellFX or Cryosurgical treatment as assessed by the blinded site investigator. The skin change safety event is defined as the presence of hyperpigmentation, hypopigmentation, or scarring. The timing of the evaluation of this endpoint is wart specific as some warts may not require multiple treatments with CellFX or Cryosurgery. Warts will be

categorized as having a skin change safety event if any component (hyperpigmentation, hypopigmentation, or scarring) is present at the follow-up visit 90 days after the last treatment.

The statistical hypotheses to be evaluated for the skin change primary safety endpoint are:

$H_0: p_{CellFX} - p_{Cryo} \geq 15\%$ at 90 days post last treatment, versus

$H_A: p_{CellFX} - p_{Cryo} < 15\%$ at 90 days post last treatment

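### Section 6.3 gives no power for meeting all three co-primary endpoints together: at 63 evaluable subjects per arm it is about 66% if the endpoints are independent and at most about 80%, and the stated 88% fits skin change only

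*Combined protocol and SAP*

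**What the plan says.** Section 6.1 says that "this study is designed with 3 co-primary endpoints": wart clearance and wound healing events at 30 days after the last treatment, and skin changes at 90 days. It adds that "The endpoints must demonstrate non-inferiority for the study to be considered successful". Section 6.1.4 repeats the rule ("Study success requires the demonstration of non-inferiority for the primary safety and efficacy endpoints") and concludes from it that no multiplicity adjustment is needed. Each endpoint is tested through a two-sided 95% confidence interval; section 6.1.1 notes that "This approach is equivalent to a 1-sided test with a 2.5% type I error rate". Section 6.1.3 says that "non-inferiority margins of 15% were selected based on clinical judgement for the primary safety and effectiveness endpoints".

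Section 6.3 then gives one power statement for the whole design: "In order to maintain at least 88% power to test the primary hypotheses using 15% non-inferiority margins", about 97 warts (33 subjects) per arm before clustering and at least 63 subjects (189 warts) per arm after it. With about 15% loss to follow-up, 150 subjects are enrolled. The section does not say whether the 88% applies to each endpoint, to one of them or to all three jointly. It gives no power by endpoint and no correlation between endpoints.

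**The concern.** An all-must-win rule cuts both ways. It protects the type I error, so the plan is right not to adjust alpha. It also lowers power, because one failed endpoint fails the study. Section 6.3 takes the benefit and does not report the cost.

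Two questions follow. Does 88% hold for every endpoint? What is the probability of meeting all three? If 88% is neither the lowest single-endpoint power nor the joint power, anyone judging whether 150 subjects are enough is working from a figure that does not describe the success criterion. The exposure is to a failed trial, not to a false claim of non-inferiority.

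**Working it through.** **Inputs.** Sections 6.1.1 to 6.1.3: one-sided alpha 0.025 and a 15-point margin for each endpoint. Section 6.3: 3 warts per subject, equal correlation in both arms, and the following rates.

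| Endpoint | CellFX | Cryosurgery | Within-subject correlation |
|---|---|---|---|
| Clearance | 75.5% | 70% | 0.30 |
| Wound healing event | 37.6% | 43% | 0.55 |
| Skin change event | 32.5% | 40% | 0.55 |

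**Assumed by me.** Unpooled normal approximation and design effect DE = 1 + (3 − 1) × correlation, which is 1.6 for clearance and 2.1 for both safety endpoints. The plan cites methods but prints no formula.

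**Step 1: reproduce the plan's figure.** Warts per arm before clustering = (1.960 + 1.175)² × [p₁(1 − p₁) + p₂(1 − p₂)] / D², where D is the distance from the expected difference to the margin: 0.150 + 0.055 = 0.205 for clearance, 0.150 + 0.054 = 0.204 for wound healing, 0.150 + 0.075 = 0.225 for skin change. At 88% power:

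| Endpoint | Warts before clustering | × DE | Subjects per arm |
|---|---|---|---|
| Clearance | 92.4 | 147.8 | 50 |
| Wound healing | 113.3 | 237.9 | 80 |
| Skin change | 89.2 | 187.3 | 63 |

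The plan's 63 is the skin change result. The 150 also follows: 126 / 0.85 = 148.2, rounded up to 149, or 75 per arm. The 97 unclustered warts do not follow: the formula gives 93, 114 and 90. Skin change with a continuity correction gives 98, but 98 × 2.1 / 3 needs 69 subjects, not 63. The plan's own inflation, 189 / 97 = 1.95, equals neither 1.6 nor 2.1.

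**Step 2: power per endpoint at 63 per arm.** Effective warts per arm are 189 / 1.6 = 118.1 and 189 / 2.1 = 90.0. Power = Φ(D / SE − 1.960), with SE = √(variance sum / effective warts).

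- Clearance: SE = √(0.3950 / 118.1) = 0.0578; Φ(3.545 − 1.960) = 94%.
- Wound healing: SE = √(0.4797 / 90.0) = 0.0730; Φ(2.794 − 1.960) = 79.8%.
- Skin change: SE = √(0.4594 / 90.0) = 0.0714; Φ(3.149 − 1.960) = 88.3%.

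Pooled variance leaves wound healing at 79.7%; a continuity correction lowers it to 75.2%. One-sided alpha of 0.05 brings it to 87.5%, but contradicts the stated 2.5%.

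**Step 3: joint power.** The plan gives no between-endpoint correlation, so I show the range.

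| Dependence between test statistics | 63 per arm | 75 per arm |
|---|---|---|
| Independent (product) | 66.5% | 77.9% |
| Common correlation 0.2 | 68.6% | 79.0% |
| Common correlation 0.5 | 72.2% | 81.3% |
| Common correlation 0.8 | 76.7% | 84.2% |
| Lower limit, any dependence | 62.4% | 76.4% |
| Upper limit (weakest endpoint) | 79.8% | 86.2% |

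The product at 63 is 0.9435 × 0.7979 × 0.8829. The upper limit is wound healing's own power, which joint power cannot exceed.

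**Step 4: does the choice of design effect matter?** Using the plan's implied 1.95 for every endpoint means 97 effective warts, and power of 89.5%, 82.7% and 90.5%. Joint power is then 66.9% if independent and at most 82.7%. The conclusion does not change.

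**The case against.** The best defence has four parts.

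First, section 6.3 never says that 88% is joint, nor that it holds endpoint by endpoint. That is true, and a reader who infers that 88% is the power of each endpoint goes beyond the text: the figure matches skin change alone. The defence does not rescue the sentence, however, because the words at least 88% fail for wound healing on one reading and for joint power on the other.

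Second, independence is the plan's assumption nowhere. Scarring is a component of both safety composites, scored on the same warts, so positive correlation is plausible. This stands. A reader might infer that 66%, or a failure risk of one in three, follows from the plan's inputs alone. It does not: the documents support only a range, with a failure risk of 20% to 38% at 63 per arm.

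Third, part of the shortfall is the wound healing figure and not the joint requirement. This also stands. With wound healing at 88% and the other two unchanged, joint power under independence would be 0.9435 × 0.88 × 0.8829 = 73%. The part due purely to requiring three endpoints is shown by 0.88³ = 68% for three independent endpoints at exactly 88%. The two should not be counted as wholly separate defects.

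Fourth, type I error, the estimand and the analysis are untouched, and my formula does not recover the 97 warts. Both are correct. The second limits certainty about how the sponsor calculated, but Step 4 shows that the result survives the plan's own inflation factor.

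**Conclusion.** The power statement in section 6.3 is wrong as written. At 63 evaluable subjects per arm, power is about 94% for clearance, 80% for wound healing and 88% for skin change. Power for the success criterion is about 66% if the endpoints are independent, about 69% to 77% at assumed common correlations of 0.2 to 0.8, and 62% to 80% under any dependence. Even with no loss (75 per arm) it is about 78% if independent and cannot exceed 86%.

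This rests on the plan's event rates, all of which favour CellFX, on 3 warts per subject, and on the normal approximation and design effect stated above. The position within the range depends on a between-endpoint correlation that the documents do not supply. Nothing here shows that 150 subjects is an unacceptable choice; it shows that the choice is not described by the figure given.

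**What to change.** In section 6.3, replace the single 88% statement with a short table: power for each co-primary endpoint and joint power for all three, at 63 and at 75 evaluable subjects per arm, over a stated range of between-endpoint correlation. State the formula and design effect used, and reconcile the 97 warts, the 63 subjects and the 88%.

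A row for no true difference (70%, 43% and 40% in both arms) is optional. At 63 per arm, joint power there is about 20% if independent, 25% to 33% at correlations of 0.2 to 0.5, and at most 53%.

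The cost is one table, one sentence and a less favourable stated figure. The sample size need not change. Should the sponsor want more, the same formula gives 80 evaluable per arm (189 enrolled at 15% loss) for 88% on every endpoint, with joint power of about 82% if independent, and 92 per arm (217 enrolled) for 88% joint power under independence.
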